9.7 Reporting of Serious Adverse Effects

The Study Site PI, or delegate is required to promptly notify the Sponsor of the following events:

- Any unanticipated problems including serious adverse events involving risks to participants or others which occur at the study site, or that impacts participants or the conduct of the study.
- Noncompliance with federal regulations or the requirements or determinations of the Sponsor.
- Receipt of new information that may impact the willingness of participants to participate or continue participation in the research study.

Any SAE must be reported by the investigator if it occurs during the clinical study or within 1 day of receiving the LSALT peptide, whether or not the SAE is considered to be related to the LSALT peptide. An SAE report consists of the SAE report form, and where applicable the concomitant medication/history form. A copy of these forms must be emailed or faxed within 24 hours for the attention of the Sponsor's safety representative:

Attention Syneos Health Safety & Pharmacovigilance
Email: [contact] (preferred)
Local Toll-Free Fax (Australia): [name]
Alternate (Global) [contact]

The investigator should not wait to receive additional information to document fully the event before notification of a SAE, though additional information may be requested. Where applicable, information from relevant laboratory results, hospital case records, and autopsy reports should be obtained and provided upon request.

9.8 Protocol Exceptions

A planned deviation from the approved protocol that are under the research team's control must be approved by the sponsor and ethics committee. Waivers are not acceptable.

9.9 Unblinding

Adverse events Grade 2 or greater will trigger unblinding to allow study personnel and the PI to best manage the study participant and clinical situation.

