6.4 Blinding

Participants and the study investigators/personnel will be blinded. This is a third-party blinded study whereupon the pharmacist (or designate) preparing the LSALT peptide or placebo for infusion will be unblinded.

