9.3 Assessment of Causality

All AEs (both serious and nonserious) will be assessed for relationship to investigational product by the Investigator. The investigator will assess the relationship of AEs to investigational product administration using the following categories:

Unrelated: The AE is clearly not related to the LSALT peptide and is clearly related to an underlying disease, environmental or toxic factor(s), or other drug/therapy.

Unlikely related: The AE does not follow a reasonable temporal sequence after LSALT peptide administration (eg, too soon or too long after investigational product or investigational product was not taken) and is plausibly related to an underlying disease, environmental or toxic factor(s), or other drug/therapy. For purposes of regulatory reporting, AEs classified as unlikely related will be considered unrelated to the LSALT peptide.

Possibly related: The AE follows a reasonable temporal sequence after investigational product administration but may be related to an underlying disease, environmental or toxic factor(s), or other drug/therapy. There is a reasonable possibility of a causal relationship between investigational product administration and the AE. For purposes of regulatory reporting, AEs classified as possibly related will be considered related to investigational product.

Probably related: The AE follows a reasonable temporal sequence after LSALT peptide administration and is unlikely to be related to an underlying disease, environmental or toxic factor(s), or other drug/therapy. The AE is consistent with the known response pattern of the LSALT peptide and may respond to stopping the LSALT peptide. For purposes of regulatory reporting, AEs classified as probably related will be considered related to the LSALT peptide.

Related: The adverse event is clearly related to the LSALT peptide; a re-challenge confirms the association (not required or desirable in some circumstances but provides strong evidence when it happens).

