3.7. Randomization and Blinding

Randomization:

Computer generated randomization schedules will be prepared prior to the start of the study. The schedules will be generated through the statistical analysis system (SAS) software, version 9.4. Block randomization will be used.

This document is confidential.

Low Dose Subjects will receive only LSALT peptide. SAD and MAD subjects will be randomly assigned to receive either LSALT peptide or matching placebo in a ratio of 3:1 (active: placebo). A Randomization Plan will be created (which includes provisions for replacement subjects), and the randomization of eligible study participants will be managed as per the plan.

In the event of participant drop-out, participants from the reserve pool will be enrolled in the study and randomized. For subjects who are replaced the replacements should take the same treatment assignment as the original subject to ensure that the planned treatment allocation ratio is retained.

Blinding:

Participants and the study investigators/personnel will be blinded except for initial low doses of LSALT in single subjects which will be open-label. This is a third-party blinded study whereupon the pharmacist (or designate) preparing the LSALT peptide or placebo for infusion will be unblinded.

This document is confidential.

4. Endpoints

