10.2. Adverse Events

Adverse events will be coded using the Medical Dictionary for Regulatory Activities (MedDRA) version 21.0 or higher. AEs will be grouped by system organ class (SOC) and preferred term (PT) and summarized by actual treatment. The summary tables will present the number and percentage of total subjects and number of events by SOC and by PT.

All AE summaries will be restricted to treatment emergent AEs (TEAEs) only. Treatment emergent AEs are defined as AEs that commence on or after the time of first study drug administration. Adverse events without an onset date or time or AEs with an onset date of the date of first study drug administration but without an onset time will be defined as treatment emergent, except if an incomplete date (e.g., month and year) clearly indicates that the event started prior to administration of first study drug or if the AE stop date indicates that the event started and stopped prior to administration of first study drug.

Treatment-emergent AEs will be summarized by actual treatment. The number and percentage of subjects experiencing AEs and the number of TEAEs will be tabulated. Subjects who experience the same AE (in terms of MedDRA preferred term) more than once will only be counted once for that event, however, the total number of events will also be counted per category. This also applies to sub-categories displayed in the summaries.

The following summaries will be presented:

- Overall summary of TEAEs
- TEAEs by SOC and PT
- TEAEs by SOC, PT, and severity
- TEAEs by SOC, PT, and relationship to study drug
- Serious TEAEs by SOC and PT

All AEs will be listed. This will include a separate listing of serious adverse events (SAEs), and Non-TEAEs.

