	All Placebo (N=xxx) S (%) E	LSALT 1.0 mg (N=xxx) S (%) E	etc. (N=xxx) S (%) E
At Least One TEAE	xx (xx.x%) xx	xx (xx.x%) xx	xx (xx.x%) xx
At Least One Severe or Life-threatening TEAE	xx (xx.x%) xx	xx (xx.x%) xx	xx (xx.x%) xx
At Least One Study Drug-related[1] TEAE	xx (xx.x%) xx	xx (xx.x%) xx	xx (xx.x%) xx
At Least One Serious TEAE	xx (xx.x%) xx	xx (xx.x%) xx	xx (xx.x%) xx
At Least One Serious Study Drug-related[1] TEAE	xx (xx.x%) xx	xx (xx.x%) xx	xx (xx.x%) xx
Discontinuation Due to TEAE	xx (xx.x%) xx	xx (xx.x%) xx	xx (xx.x%) xx
Death	xx (xx.x%) xx	xx (xx.x%) xx	xx (xx.x%) xx

S = Subjects, E = Events.

TEAE = Treatment Emergent Adverse Event.

[1] Drug-related is defined as Missing, Possibly, Probably or Related.

Table 14.3.1.1.3 Treatment Emergent Adverse Events Overall Summary - MAD (Safety Population)

	All Placebo (N=xxx) S (%) E	LSALT XX mg (N=xxx) S (%) E	etc. (N=xxx) S (%) E
At Least One TEAE	xx (xx.x%) xx	xx (xx.x%) xx	xx (xx.x%) xx
At Least One Severe or Life-threatening TEAE	xx (xx.x%) xx	xx (xx.x%) xx	xx (xx.x%) xx
At Least One Study Drug-related[1] TEAE	xx (xx.x%) xx	xx (xx.x%) xx	xx (xx.x%) xx
At Least One Serious TEAE	xx (xx.x%) xx	xx (xx.x%) xx	xx (xx.x%) xx
At Least One Serious Study Drug-related[1] TEAE	xx (xx.x%) xx	xx (xx.x%) xx	xx (xx.x%) xx
Discontinuation Due to TEAE	xx (xx.x%) xx	xx (xx.x%) xx	xx (xx.x%) xx
Death	xx (xx.x%) xx	xx (xx.x%) xx	xx (xx.x%) xx

S = Subjects, E = Events.

TEAE = Treatment Emergent Adverse Event.

[1] Drug-related is defined as Missing, Possibly, Probably or Related.

Table 14.3.1.2.2 Treatment Emergent Adverse Events - SAD (Safety Population)

System Organ Class Preferred Term	All Placebo (N=xxx) S (%) E	LSALT 1.0 mg (N=xxx) S (%) E	etc. (N=xxx) S (%) E
Subjects with at Least One TEAE	xx (xx.x%) xx	xx (xx.x%) xx	xx (xx.x%) xx
System Organ Class 1	xx (xx.x%) xx	xx (xx.x%) xx	xx (xx.x%) xx
Preferred Term 1	xx (xx.x%) xx	xx (xx.x%) xx	xx (xx.x%) xx
Preferred Term 2	xx (xx.x%) xx	xx (xx.x%) xx	xx (xx.x%) xx
System Organ Class 2	xx (xx.x%) xx	xx (xx.x%) xx	xx (xx.x%) xx
Preferred Term 1	xx (xx.x%) xx	xx (xx.x%) xx	xx (xx.x%) xx
Preferred Term 2	xx (xx.x%) xx	xx (xx.x%) xx	xx (xx.x%) xx
etc.			

S = Subjects, E = Events.

TEAE = Treatment Emergent Adverse Event.

Note: Subjects are counted once if the same event occurred more than one time.

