Probably Related	xx (xx.x%) xx	xx (xx.x%) xx	xx (xx.x%) xx
Related	xx (xx.x%) xx	xx (xx.x%) xx	xx (xx.x%) xx
Missing	xx (xx.x%) xx	xx (xx.x%) xx	xx (xx.x%) xx
etc.			

S = Subjects, E = Events.

TEAE = Treatment Emergent Adverse Event.

Note: Subjects are counted once if the same event occurred more than one time.

Note: This table presents the number of subjects with an event, the percentage of total subjects with an event and the number of events. Percentages are based on the total number of treated subjects.

Note: Adverse events coded according to MedDRA Version XX.

Table 14.3.1.4.3 Treatment Emergent Adverse Events by Relationship to Study Drug - MAD (Safety Population)

System Organ Class Preferred Term Relationship to Study Drug	All Placebo (N=xxx) S (%) E	LSALT XX mg (N=xxx) S (%) E	etc. (N=xxx) S (%) E
Subjects with at Least One TEAE			
Unrelated	xx (xx.x%) xx	xx (xx.x%) xx	xx (xx.x%) xx
Unlikely Related	xx (xx.x%) xx	xx (xx.x%) xx	xx (xx.x%) xx
Possibly Related	xx (xx.x%) xx	xx (xx.x%) xx	xx (xx.x%) xx
Probably Related	xx (xx.x%) xx	xx (xx.x%) xx	xx (xx.x%) xx
Related	xx (xx.x%) xx	xx (xx.x%) xx	xx (xx.x%) xx
Missing	xx (xx.x%) xx	xx (xx.x%) xx	xx (xx.x%) xx
System Organ Class 1			
Preferred Term 1	xx (xx.x%) xx	xx (xx.x%) xx	xx (xx.x%) xx
Unrelated	xx (xx.x%) xx	xx (xx.x%) xx	xx (xx.x%) xx
Unlikely Related	xx (xx.x%) xx	xx (xx.x%) xx	xx (xx.x%) xx
Possibly Related	xx (xx.x%) xx	xx (xx.x%) xx	xx (xx.x%) xx
Probably Related	xx (xx.x%) xx	xx (xx.x%) xx	xx (xx.x%) xx
Related	xx (xx.x%) xx	xx (xx.x%) xx	xx (xx.x%) xx
Missing	xx (xx.x%) xx	xx (xx.x%) xx	xx (xx.x%) xx
etc.			

S = Subjects, E = Events.

TEAE = Treatment Emergent Adverse Event.

Note: Subjects are counted once if the same event occurred more than one time.

Note: This table presents the number of subjects with an event, the percentage of total subjects with an event and the number of events. Percentages are based on the total number of treated subjects.

Note: Adverse events coded according to MedDRA Version XX.

Table 14.3.1.5.2 Serious Treatment Emergent Adverse Events - SAD (Safety Population)

System Organ Class Preferred Term	All Placebo (N=xxx) S (%) E	LSALT 1.0 mg (N=xxx) S (%) E	etc. (N=xxx) S (%) E
Subjects with at Least One Serious TEAE	xx (xx.x%) xx	xx (xx.x%) xx	xx (xx.x%) xx
System Organ Class 1	xx (xx.x%) xx	xx (xx.x%) xx	xx (xx.x%) xx
Preferred Term 1	xx (xx.x%) xx	xx (xx.x%) xx	xx (xx.x%) xx
Preferred Term 2	xx (xx.x%) xx	xx (xx.x%) xx	xx (xx.x%) xx

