Subject Number	Subject Eligible for Randomization	Randomization Date/ Time	Randomization Number	Cohort: Treatment Group
xxxxx	Yes	DDMONTHYYYY/ HH:MM	xxxxx	Cohort 4: Placebo
etc.				

Listing 16.2.7.1.1 Adverse Events - Low Dose (Intent-to-Treat Population)

Treatment Group: LSALT 0.01 mg

Subject Number	Date/ Time of Study Drug Administration	System Organ Class/ Preferred Term/ Adverse Event		Onset Date/ Time/ Study Day	Resolution Date/ Time Study Day	Severity	Relationship to Study Drug	Outcome	Action Taken with Study Drug	Concomitant Medication Administered	TEAE[1]
		SAE									
xxxxx	DDMONYYYY/ HH:MM	XXXXXXXXXXXX/ YYYYYYYYYYYY/ ZZZZZZZZZZZZZ	No	DDMONYYYY/ HH:MM/ XX	DDMONYYYY/ HH:MM/ XX	Mild	Related	Recovering /Resolving	Study Drug Stopped	No	Yes
		XXXXXXXXXXXX/ YYYYYYYYYYYY/ ZZZZZZZZZZZZZ	Yes	DDMONYYYY/ HH:MM/ XX	DDMONYYYY/ HH:MM/ XX	Moderate	Unrelated	Unknown	Unkown	Yes	Yes

Adverse Events coded using MedDRA Version X.X.

[1] TEAE = Treatment Emergent Adverse Event.

Listing 16.2.7.1.2 Adverse Events - SAD (Intent-to-Treat Population)

Cohort/Treatment Group: Cohort 1/Placebo

Subject Number	Date/ Time of Study Drug Administration	System Organ Class/ Preferred Term/ Adverse Event	Onset Date/ Time/ Study Day	Resolution Date/ Time/ Study Day	Relationship to Study Drug	Action Taken with Study Drug	Concomitant Medication Administered	TEAE[1]
SAE			Severity		Outcome			
xxxxx	DDMONYYYY/ HH:MM	XXXXXXXXXXXX/ YYYYYYYYYYYY/ ZZZZZZZZZZZZ	No	DDMONYYYY/ HH:MM/ XX	DDMONYYYY/ HH:MM/ XX	Mild Related Recovering /Resolving	Study Drug Stopped	No Yes
		XXXXXXXXXXXX/ YYYYYYYYYYYY/ ZZZZZZZZZZZZ	Yes	DDMONYYYY/ HH:MM/ XX	DDMONYYYY/ HH:MM/ XX	Moderate Unrelated Unknown	Unknown	Yes Yes

etc.

Adverse Events coded using MedDRA Version X.X.

[1] TEAE = Treatment Emergent Adverse Event.

Listing 16.2.7.1.3 Adverse Events - MAD (Intent-to-Treat Population)

Cohort/Treatment Group: Cohort 4/Placebo

Subject Number	Date/ Time of Study Drug Administration	System Organ Class/ Preferred Term/ Adverse Event	Onset Date/ Time/ Study Day	Resolution Date/ Time/ Study Day	Relationship to Study Drug	Action Taken with Study Drug	Concomitant Medication Administered	TEAE[1]
SAE			Severity		Outcome			
xxxxx	DDMONYYYY/ HH:MM	XXXXXXXXXXXX/ YYYYYYYYYYYY/ ZZZZZZZZZZZZ	No	DDMONYYYY/ HH:MM/ XX	DDMONYYYY/ HH:MM/ XX	Mild Related Recovering /Resolving	Study Drug Stopped	No Yes

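### Protocol 9.9 unblinds the investigator at any Grade 2 or higher adverse event, and neither document requires causality to be recorded before the code is opened (low priority, cheap to improve).

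*Protocol*

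**What the plan says.** Protocol 9.9 is one sentence: "Adverse events Grade 2 or greater will trigger unblinding to allow study personnel and the PI to best manage the study participant", and it goes on to mention the clinical situation. It sets no condition on seriousness, relatedness or need, and says nothing about what must be documented first.

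Protocol 9.3 assigns causality to the same person: "All AEs (both serious and nonserious) will be assessed for relationship to investigational product by the Investigator". Most of its five categories are worded against the LSALT peptide itself. No time point is given.

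On blinding, Protocol 6.4 says "Participants and the study investigators/personnel will be blinded", and SAP 3.7 says "Participants and the study investigators/personnel will be blinded except for initial low doses of LSALT in single subjects which will be open-label". Neither refers to 9.9.

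The rating is used in two sets of outputs. SAP 10.2 lists "TEAEs by SOC, PT, and relationship to study drug" among the planned summaries (shells 14.3.1.4.2 and 14.3.1.4.3). The overall summary shells (14.3.1.1.2 and 14.3.1.1.3) have drug-related rows with the footnote "Drug-related is defined as Missing, Possibly, Probably or Related".

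**The concern.** Of the attributes of an adverse event, relatedness is the one most open to knowledge of treatment. The categories ask whether the LSALT peptide caused the event, so once the Investigator knows the participant had placebo, the question is largely answered. A participant known to be on active drug can still be rated possibly, probably or definitely related. The relationship tables invite a comparison of placebo with LSALT, and for events rated after a break that comparison is no longer blinded. The events concerned are Grade 2 or higher, which are the ones a reader will look at first.

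This goes beyond missing detail, because a stated automatic rule creates the exposure. A blank rating is not neutral either, since the footnote counts missing as drug-related.

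**Working it through.** **Is there an ordering rule anywhere?** I read the relevant sections side by side.

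| Place | Subject | Causality before break? |
|---|---|---|
| Protocol 6.4 | Blinding | Silent |
| Protocol 8.0 | Pause and termination | Silent; counts by grade |
| Protocol 9.2, 9.5, 9.7 | Grading, SAEs, SAE reporting | Silent |
| Protocol 9.3 | Causality | No time point |
| Protocol 9.9 | Unblinding | Silent |
| Protocol 14.0 | Safety monitoring | Silent |
| SAP 3.7, 10.2 | Blinding, adverse event analysis | Silent |
| SAP 5 (opening) | Analysis populations fixed before final unblinding | Does not concern causality |

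**What can a reader see?** The adverse event listing shells (16.2.7.1.2 and 16.2.7.1.3) show treatment group, subject, onset date and time, severity and relationship. Because the trigger is automatic on grade, every rating at risk can be picked out. The shells have one relationship field, no time of entry and no code-break column, so the order of rating and break is not shown. SAP 6.1 lists everything in the database, so a break date would appear if the eCRF captures one.

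**How many breaks?** The documents give no Grade 2 or higher rate, so the rates p below are assumptions, counting at most one break per participant.

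- Blinded participants (Protocol 7.1.1 and 7.2.1; SAP 3.5): 3×8 + 3×8 = 48.
- Protocol 3.7 says six cohorts are complete, and 3.8 proposes a third MAD cohort. Counting the low-dose group as one of the six, 3×8 + 2×8 = 40 blinded participants are done and 48 − 40 = 8 remain.
- Expected breaks = n×p. Chance of at least one among 8 = 1 − (1 − p)^8.

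| Assumed p | Expected, 8 remaining | At least one in 8 | Expected, all 48 |
|---|---|---|---|
| 2% | 0.16 | 15% | 0.96 |
| 5% | 0.40 | 34% | 2.4 |
| 10% | 0.80 | 57% | 4.8 |
| 20% | 1.6 | 83% | 9.6 |

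Fewer than one break is expected among the 8 for any p below 1/8 = 12.5%. As a rough guide to p, suppose Protocol 3.7's report of no significant adverse effects means no Grade 2 or higher event in the 3×6 + 2×6 = 30 LSALT recipients at 1 mg or more. The one-sided 95% upper limit is then 1 − 0.05^(1/30) = 9.5%, and 8 × 0.095 = 0.76 breaks.

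**Who else is revealed?** SAP 3.6 allocates each blinded cohort as a 1:1 sentinel pair plus 5 LSALT and 1 placebo. Unblinding either sentinel reveals the other. Unblinding the single non-sentinel placebo reveals the other five non-sentinels as active. If each of the 8 is equally likely to be the first unblinded, (2 + 1)/8 = 37.5% of first breaks fix at least one other participant's arm.

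**The case against.** The strongest case against acting is materiality. Overall adverse event incidence (SAP 4.1) and the pause and termination rules (Protocol 8.0) do not use causality. Reporting is descriptive (Protocol 16.0). On the assumed rates, very few ratings are affected. All of this stands, and it sets the priority.

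The gap is also silence in two documents, and does not prove that a control is absent. SAP 2 names eCRF version 4.00 and a protocol addendum, and Protocol 6.3 names a Randomization Plan. None was available, and any of them could fix the order. That stands too.

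A reader might infer more than the documents support:

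- *That ratings made before and after a break are pooled beyond recovery.* The listings identify every Grade 2 or higher rating, which a reader can discount. Only the order is missing.
- *That 9.9 contradicts the blinding sections.* It reads as a specific exception to them.
- *That the pre-break rating should replace the final one in the tables.* Protocol 9.3 uses response to stopping the peptide and the result of any re-challenge, which may be known only later. A later rating may be better informed as well as less blinded, so both should be shown.

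What remains is that a stated rule lets causality be rated with treatment known, and the planned outputs cannot show when that happened.

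**Conclusion.** The point holds as a low-priority improvement. As written, the plan lets relatedness of a triggering event be assigned after the code is opened, with no record of the order. The effect is confined to the relationship tables and the drug-related rows. It does not support a claim that the primary safety incidence or the escalation decisions are biased.

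The size rests on assumptions: the per-participant rates, the reading of Protocol 3.7 as no Grade 2 or higher event, and the count of 8 remaining. That count treats the low-dose group as a cohort. SAP 3.6 leaves it unnumbered and numbers the blinded cohorts 1 to 6, but the proposal of a third MAD cohort in Protocol 3.8 favours the reading used here. A change to 9.9 acts only on participants still to be dosed, whereas the SAP and listing changes cover all 48.

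**What to change.** Leave the trigger and access to the code for care unchanged.

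- **Protocol 9.9:** add that event term, grade and causality are recorded with date and time before the code is opened wherever this does not delay care, and that the date and time of every break are recorded.
- **SAP 10.2 and the adverse event listings:** add the break date and time. Flag causality first entered or revised after the break, or where the order cannot be shown. List the pre-break and final ratings side by side, without making the pre-break rating the primary tabulated value.
- **Deduction:** flag any other participant whose arm is revealed, meaning the sentinel partner or, if the single non-sentinel placebo is unblinded, the other five non-sentinels.

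The cost is a short documentation step, one or two listing columns, and a footnote for completed cohorts with no captured pre-break rating. eCRF fields are needed only if version 4.00 lacks them. If an unseen document already sets the order, only the SAP and listing text remains to be done.

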10.0 PHARMACEUTICAL INFORMATION

10.1 LSALT Peptide

10.1.1 LSALT Peptide Description.

LSALT is an unmodified peptide with the molecular formula: Leu-Ser-Ala-Leu-Thr-Pro-Ser-Pro-Ser-Trp-Leu-Lys-Tyr-Lys-Ala-Leu

Molecular weight: 1775 Da

10.1.2 Mechanism of Action

LSALT peptide is a non-enzymatic inhibitor of dipeptidase-1

10.1.4 Dosage

Supplied as 1 mg/ml solution in 5 ml 0.9% sodium chloride. Dosages for this study are 0.01 mg, 0.1 mg, 0.3 mg, 0.5 mg, 1.0 mg, 2.5 mg and 5 mg.

10.1.5 Storage

LSALT peptide in 0.9% sodium chloride is stored at -20° C and thawed immediately before use as per pharmacy manual.

10.1.6 Administration

LSALT peptide is diluted in 100 ml of 0.9% sodium chloride and administered intravenously over 2 hours ± 5 minutes. Based upon evaluation of tolerability and safety of the first cohort, and consistent with the adaptive design, infusion rates could be increased or decreased for subsequent cohorts, as determined by the SRC.

11.0 MONITORING AND QUALITY

Data for each subject will be recorded on an eCRF. Data collection must be completed for each subject who signs an informed consent form (ICF) and is administered study drug. In accordance with cGCP and ICH guidelines, the study monitor will carry out source document verification at regular intervals to ensure that the data collected in the CRF are accurate and reliable. The investigator must permit the monitor, the IEC/IRB, the sponsor's internal auditors, and representatives from regulatory authority's direct access to all study-related documents and pertinent hospital or medical records for confirmation of data contained within the CRFs.

